4 STUDY SYNOPSIS

Name of Sponsor/Company: Golden Biotechnology Corporation	Individual Study Table Referring to Part of the Dossier: Volume: Page:	(For National Authority Use Only)
Name of Product: Hocena [®] 100 mg capsule		
Name of Active Ingredient: Antroquinonol		
Title of Study: A single-arm, open-label, Phase II study evaluating the efficacy, safety and pharmacokinetics of antroquinonol in patients with stage IV (including pleural effusion) non-squamous non-small cell lung cancer (NSCLC) who have failed two lines of anti-cancer therapy		
Principle Investigator: [name]; Johns Hopkins Sidney Kimmel Comprehensive Cancer Center, [name], [name], United States of America (USA).		
Study Centers: It is planned that at least 10 centers will be initiated for this study in the USA (nine centers) and Taiwan (one center).		
Publications: None.		
Planned Study Period: Third quarter, 2013 to fourth quarter, 2016	Development Phase: Phase II	
Objectives: Primary Objective: To evaluate the activity of antroquinonol in unselected, KRAS-positive, and KRAS-negative patients with stage IV (including pleural effusion) non-squamous NSCLC who have failed two lines of anti-cancer therapy. Secondary Objective: To assess the safety and tolerability and pharmacokinetics (PK) of antroquinonol in patients with stage IV (including pleural effusion) non-squamous NSCLC who have failed two lines of anti-cancer therapy. Exploratory Objective: To explore potential relationships between of antroquinonol exposure and safety and efficacy endpoints.		
Methodology: This is a single-arm, open-label, Phase II study in KRAS-positive and KRAS-negative patients with stage IV (including pleural effusion) non-squamous NSCLC who have failed two lines of anti-cancer therapy. This is defined as patients with radiologically confirmed disease progression following greater than or equal to two, but less than or equal to four, prior lines of systemic anti-cancer therapy (see Inclusion Criteria). A maximum of 60 evaluable patients with NSCLC will receive antroquinonol, of which 30 patients will be KRAS-positive and 30 patients KRAS-negative. An evaluable patient will have received at least one dose of antroquinonol and have a valid baseline tumor assessment (see Statistical Methods). Enrollment will continue until the target number of evaluable patients has been enrolled. Written informed consent must be obtained from all patients before initiating Screening. The Screening period will be up to 42 days in duration (Days -42 to -1). Following completion of all Screening assessments and confirmation of eligibility criteria, patients will receive antroquinonol 200 mg three times a day (t.i.d. at 8-hour intervals) on Day 0 for 12 weeks (one treatment cycle) or until documented evidence of disease progression, unacceptable toxicity, non-compliance or withdrawal of consent by the patient, or the investigator decides to discontinue treatment, whichever comes first. Study drug should be taken at 8-hour intervals. The time of study drug administration should be recorded in the patient diary. After the first 12-week treatment cycle, patients who are progression-free will be eligible to receive further (12-week) treatment cycles with antroquinonol (Extension Phase), until documented evidence of disease progression, unacceptable toxicity, non-compliance or withdrawal of consent by the patient, or the investigator decides to discontinue treatment, whichever comes first. Patients will attend study visits on Days 0, 14, 28, 42, 56 and 84 during the first 12-week treatment cycle, every 4 weeks during the second, third, and fourth treatment cycles (Extension Phase), and every 12 weeks during		

Name of Sponsor/Company: Golden Biotechnology Corporation	Individual Study Table Referring to Part of the Dossier: Volume: Page:	(For National Authority Use Only)
Name of Product: Hocena [®] 100 mg capsule		
Name of Active Ingredient: Antroquinonol		

subsequent treatment cycles (Extension Phase).
 
The study-specific procedures include: physical examination, vital signs, 12-lead electrocardiogram (ECG), performance status, clinical laboratory tests, adverse events (AEs), concomitant medication and patient compliance.
 
Patients discontinuing the study will attend an End of Study Visit, 4 weeks after the last administration of study drug.
 
Intensive PK sampling will be performed on Days 0 and 28 in all patients enrolled in Stage 1. Sparse PK sampling will be performed on Days 28, 42, and 56 in all patients enrolled in Stage 2.
 
All patients who discontinue from study drug, but consent to be followed up for survival status, will be followed up by telephone contact every 3 months, for a maximum of 6 months from the date of last administration of study drug or death, whichever occurs first.
 
Tumor assessments will be performed at Screening, Day 42 and Day 84 using the Response Evaluation Criteria in Solid Tumors (RECIST) criteria version 1.1. Tumor assessments will be performed every 12 weeks during the Extension Phase.
 
The primary efficacy endpoint is progression-free survival (PFS) rate at 12 weeks, which is defined as the proportion of patients alive and progression-free at Week 12. Patients will be progression-free if they have no evidence of progressive disease (defined according to RECIST guidelines, version 1.1) from the start of treatment to Week 12.
 
The study uses a two-stage design seeking to detect a true PFS rate of more than 35% in the overall (unselected) population and 40% within the KRAS tumor mutation positive and negative strata. Thirty evaluable patients (15 in each stratum) will be treated initially (Stage 1), with expansion to a maximum of 60 evaluable patients (Stage 2). The rules for continuing the overall study and individual stratum are given in the Statistical Methods below.
 
An Independent Data Monitoring Committee will act in an advisory capacity to monitor patient safety and efficacy data from the study. The members will be selected on the basis of relevant experience and understanding of clinical research and the issues specific to the therapeutic area, as well as previous data monitoring committee experience.
		

Number of Patients:
 
The study uses a two-stage design. Thirty evaluable patients (15 in each stratum) will be treated initially (Stage 1), with expansion to a maximum of 60 evaluable patients (Stage 2). Enrollment will continue until the target number of evaluable patients has been enrolled.
		

Diagnosis and Main Criteria for Inclusion:
 
Inclusion criteria
 
Patients eligible for enrollment in the study must meet all of the following criteria:
 
 • Cytologically or histologically confirmed non-squamous NSCLC Stage IV (including pleural effusion). • Radiologically confirmed disease progression following greater than or equal to two, but less than or equal to four, prior lines of systemic anti-cancer therapy, one of which should be a platinum-based regimen, OR the patient has refused treatment with approved treatment modalities, OR the investigator feels that the patient is not a candidate for other systemic therapy. Patients with epidermal growth factor receptor (EGFR)-positive mutations should have been offered treatment with an EGFR-TK inhibitor prior to enrolment in this study. Adjuvant therapy with or without maintenance therapy would count as one line of systemic therapy. A line of therapy requires at least two 3-4 week complete cycles unless it was stopped due to toxicity, in which case it would count as one line of therapy • At least one radiologically measurable target lesion per RECIST version 1.1 • Fresh or archival biopsy tissue available to determine KRAS tumor mutation status • At least 18 years of age at the time of signing informed consent • Life expectancy of at least 3 months 		

Name of Sponsor/Company: Golden Biotechnology Corporation	Individual Study Table Referring to Part of the Dossier:	(For National Authority Use Only)
Name of Product: Hocena [®] 100 mg capsule	Volume:	
Name of Active Ingredient: Antroquinonol	Page:	

 • Written informed consent that is consistent with International Conference on Harmonisation Tripartite Guideline on Good Clinical Practice guidelines • Patient or legally acceptable representative has granted written informed consent before any study-specific procedures (including special Screening tests) are performed • Eastern Cooperative Oncology Group (ECOG) performance score of 0, 1 or 2 • Hemoglobin ≥ 9.0 g/dL; platelets $\geq 100 \times 10^9/L$; absolute neutrophil count $\geq 1.5 \times 10^9/L$ without the use of hematopoietic growth factors • Bilirubin and creatinine less than $2 \times$ upper limit of normal (ULN) for the institution • Albumin ≥ 2.5 g/dL • Aspartate aminotransferase and alanine aminotransferase less than $5 \times$ ULN for the institution • Prothrombin time less than $1.5 \times$ ULN for the institution • Potassium, magnesium and phosphorus within the normal range for the institution (supplementation is permissible) • Willing to use two medically accepted and effective methods of contraception from the list below during the study (both men and women as appropriate) and for 3 months after the last dose of study drug: 
 – Established use of oral, injected or implanted hormonal methods of contraception. – Placement of an intrauterine device or intrauterine system. – Barrier methods of contraception: Condom or Occlusive cap (diaphragm or cervical/vault caps) with spermicidal foam/gel/film/cream/suppository. – Male sterilization (with the appropriate post-vasectomy documentation of the absence of sperm in the ejaculate). – True abstinence: When this is in line with the preferred and usual lifestyle of the patient. • Recovery to \leq Grade 1 or baseline of any toxicities due to prior treatments, excluding alopecia 
Exclusion criteria
 
Patients meeting any of the following criteria must not be enrolled in the study:
 
 • Chemo-, hormone- or immunotherapy, within 4 weeks or within less than four half-lives of the date of first administration of study drug and/or persistence of toxicities of prior anti-cancer therapies which are deemed to be clinically relevant • Radiotherapy within the past 2 weeks prior to the date of first administration of study drug • Previous treatment with an histone deacetylase inhibitor or an EGFR inhibitor within at least 4 weeks of the date of first administration of study drug • Treatment with any drug(s) known to be a strong inhibitor or inducer of cytochrome P450 (CYP)2C19, CYP3A4, CYP2C8, and CYP2E1, within 14 days of the date of first administration of study drug • Brain metastases which are symptomatic; patients with treated brain metastases are eligible with stable brain disease for at least 4 weeks without the requirement for steroids or anti-epileptic therapy • Inability to swallow oral medications or a recent acute gastrointestinal disorder with diarrhea e.g., Crohn's disease, malabsorption, or Common Terminology Criteria for Adverse Event (CTCAE) Grade > 2 diarrhea of any etiology at baseline • Other malignancies diagnosed within the past five years (other than curatively treated cervical cancer in situ, non-melanoma skin cancer, superficial bladder tumors Ta [non-invasive tumor] and TIS [carcinoma in situ], or non-metastatic prostate cancer stage 1 to 2, which has been previously treated with surgery or radiation therapy, and serum prostate-specific antigen is within normal limits [test performed within the past 12 months prior to the date of first administration of study drug]) • Patients with any serious active infection (i.e., requiring an intravenous antibiotic, antifungal, or antiviral agent) • Patients with known human immunodeficiency virus, active hepatitis B or active hepatitis C 		

Name of Sponsor/Company: Golden Biotechnology Corporation	Individual Study Table Referring to Part of the Dossier: Volume: Page:	(For National Authority Use Only)
Name of Product: Hocena [®] 100 mg capsule		
Name of Active Ingredient: Antroquinonol		

 • Patients who have any other life-threatening illness or organ system dysfunction, which in the opinion of the investigator, would either compromise patient safety or interfere with the evaluation of the safety of the study drug • Known or suspected substance abuse or alcohol abuse • Women of child-bearing potential or men who are able to father a child unwilling to use two medically accepted and effective methods of contraception during the study (as specified in the inclusion criteria) • Pregnancy or breast feeding • Patient unable to comply with the protocol • History of clinically significant or uncontrolled cardiac disease, including congestive heart failure, angina, myocardial infarction, arrhythmia, including New York Heart Association functional classification of three 		

Test Product, Dose and Mode of Administration:
 
Antroquinonol 100 mg. Beginning on Day 0, patients will receive one 12-week cycle of antroquinonol 200 mg t.i.d. or until disease progression, unacceptable toxicity, non-compliance or withdrawal of consent by the patient, or the investigator decides to discontinue treatment, whichever comes first.
 
Study drug should be taken at 8-hour intervals with a glass of water, approximately 15 minutes after a meal or light snack, and not within ± 1 hour of drinking an ethanol-containing beverage, e.g. an alcoholic drink. The date and time of each study drug administration should be recorded in the patient diary.
 
After the first 12-week treatment cycle, patients who are progression-free will be eligible to receive further (12-week) treatment cycles with antroquinonol (Extension Phase), until documented evidence of disease progression, unacceptable toxicity, non-compliance or withdrawal of consent by the patient, or the investigator decides to discontinue treatment, whichever comes first. Investigators should wait at least 7 days after the last administration of study drug before initiating alternative treatment.
		

Reference Therapy, Dose and Duration of Administration:
 
Not applicable.
		

Duration of Treatment:
 
Patients can be treated with antroquinonol, until documented evidence of disease progression, unacceptable toxicity, non-compliance or withdrawal of consent by the patient, or the investigator decides to discontinue treatment, whichever comes first.
		

Variables:
 
The primary and secondary efficacy analyses will be based on independent centralized assessment of medical images.
 
Efficacy:
 
Primary endpoint
 
The primary endpoint is as follows:
 
 • Progression-free survival rate at 12 weeks, defined as the proportion of patients alive and progression-free at Week 12. Patients will be progression-free if they have no evidence of progressive disease (defined according to RECIST guidelines, version 1.1) from the start of treatment to Week 12. 
Tumor response will be assessed at 6-week intervals during the first treatment cycle using the RECIST criteria, version 1.1. Each patient will be assigned one of the following categories: 1) complete response (CR), 2) partial response (PR), 3) stable disease (SD), or 4) progressive disease (PD). Patients who died from any cause or discontinued the study for any reason without a post-screening or Week 12 tumor assessment will be considered as failing to respond to treatment.
 
Secondary efficacy endpoints
 
Secondary efficacy endpoints are as follows:
 
 • Objective response rate (ORR), defined as the proportion of patients whose best overall response is either CR or PR according to RECIST version 1.1. The best overall response is the best response recorded during 		

Name of Sponsor/Company: Golden Biotechnology Corporation	Individual Study Table Referring to Part of the Dossier:	(For National Authority Use Only)
Name of Product: Hocena [®] 100 mg capsule	Volume:	
Name of Active Ingredient: Antroquinonol	Page:	

the first 12-week treatment cycle.
 
 • Disease control rate (DCR), defined as the proportion of patients with a documented CR, PR and SD during the first 12-week treatment cycle according to RECIST version 1.1. • Duration of overall tumor response (DR), defined as the interval between the date of the first observation of tumor response (CR or PR) and the date of disease progression or death. • Progression-free survival defined as the time from the date of first administration of study drug to objective tumor progression by RECIST version 1.1 or death due to any cause, whichever occurs first. • Overall survival (OS) defined as the time from the date of first administration of study drug to death from any cause. • Time to progression (TTP) defined as the time from the date of first administration of study drug to objective tumor progression by RECIST version 1.1. 
Patient Reported Outcome endpoint
 
The Patient Reported Outcome (PRO) endpoint is as follows:
 
 • European Organisation for Research and Treatment of Cancer (EORTC) Quality of Life Questionnaire (QLQ) C30 (QLQ-C30) and EORTC QLQ – Lung Cancer Module (QLQ-LC13) 
Pharmacokinetics:
 
PK endpoints will be derived for intensively sampled PK profiles by non-compartmental methods and include:
 
 • C_{max}: peak concentration • C_{trough}: trough plasma concentration • T_{max}: peak time • AUC_τ: area under the plasma concentration-time curve over the 8-hour dosing interval • T_½: terminal half-life • Vz/F: apparent volume of distribution during elimination • CL/F: apparent oral clearance • T_{½, eff}: effective half-life 
If possible, PK data from all patients will be analyzed using population-based PK (PopPK) methods and post hoc estimates of antroquinonol exposure (i.e., C_{max}, C_{trough} and AUC_τ) computed for exploration of potential exposure-response relationships.
 
Safety:
 
The safety endpoints are the incidence of reported AEs and abnormal laboratory tests. Adverse events will be assessed using the National Cancer Institute (NCI) CTCAE version 4.03.
 
Tumor biomarkers:
 
Subgroup analyses will assess the predictive value of tumor biomarkers.
		
Statistical Methods:		
Sample size and power:		

The statistical design is based on literature published by Green and Dahlberg (1992), von Mehren et. al. (2012), and Hoang et. al. (2013). It is assumed that within each of the KRAS tumor mutation positive and negative strata, a PFS rate at 12 weeks of 40% and 35% overall (unselected) population will be of interest. Further testing will not be pursued if the PFS rate at 12 weeks is less than 15%.
 
Initially, 15 evaluable patients are to be accrued within each stratum. If two or more patients are alive and progression-free at Week 12 within a stratum, then an additional 15 evaluable patients will be accrued to that stratum for a total of 30 evaluable patients.
 
If nine or more patients are alive and progression-free at Week 12 within the 30 evaluable patients in the stratum then antroquinonol will be considered worthy of further study in that cohort. This design will allow a significance level of 2.8% and a power of 90.5% within each stratum.
		

Name of Sponsor/Company: Golden Biotechnology Corporation	Individual Study Table Referring to Part of the Dossier:	(For National Authority Use Only)
Name of Product: Hocena® 100 mg capsule	Volume:	
Name of Active Ingredient: Antroquinonol	Page:	

In addition to within-stratum hypothesis testing, this study is also designed to investigate the PFS rate at 12 weeks in the overall (unselected) population. If less than three patients are alive and progression-free at Week 12 in the first 20 evaluable patients and, the criterion for continuing the individual stratum are not met, then the accrual for all strata will be discontinued. Otherwise, a maximum of 40 additional evaluable patients will be entered (depending on whether any individual stratum is closed). Fifteen or more patients alive and progression-free at Week 12 out of the maximum 60 evaluable patients would warrant further study.
 
The overall design has a significance level of 2.8% (probability of falsely declaring the regimen with a 15% PFS rate at 12 weeks to warrant further study) and power 95.6% (probability of declaring the regimen with a 35% PFS rate at 12 weeks in the overall population to warrant further study).
 
Efficacy:
 
Except for the primary efficacy analysis, there will be no formal statistical testing. All data will be summarized and listed as appropriately. All efficacy endpoints will be evaluated in both the overall (unselected) population and within-stratum.
 
The primary analysis will be performed on the evaluable population. The evaluable population will consist of all enrolled patients who receive at least one dose of antroquinonol and have a valid baseline tumor assessment. A valid baseline assessment is defined as a readable scan performed within 14 (\pm 7) days of the date of first administration of study drug. For the efficacy analysis, enrollment will continue until the target number of evaluable patients has been enrolled.
 
The full analysis set (FAS) and per-protocol set (PPS) will be used for supportive efficacy analyses. The FAS will consist of patients in the evaluable population who have at least one post-baseline tumor assessment. The PPS will consist of patients in the FAS who do not have any major protocol violations.
 
The primary analysis will follow the two stage procedure, as specified in the sample size section. All secondary efficacy endpoints will be reported with category counts, percentage and 95% confidence interval (CI). All time-to-event endpoints, PFS, OS and TTP will be evaluated using Kaplan-Meier estimates and curves will be generated based on these estimates.
 
Safety:
 
All patients who are treated with at least one dose of study drug will be evaluated for safety. Safety data will be summarized for the overall (unselected) population and within-stratum. There will be no formal statistical analysis of safety data. Demographic and Screening data will be listed and summarized, as appropriate. All AEs will be coded using the Medical Dictionary for Regulatory Activities, graded using the NCI CTCAE version 4.03 and listed by patient. Treatment-emergent AEs will be summarized by treatment, severity and causal relationship to study drug. Any serious AEs will be listed separately. System organ class and preferred terms within each body system will be used for frequency summaries. Clinical laboratory data, vital signs and ECG data will be listed by patient and summarized, as appropriate.
 
Patient Reported Outcome:
 
The PRO population will consist of all patients who have completed the QLQ on Day 0 and on at least one occasion after the first administration of study drug. All data will be summarized and listed, as appropriate. Patient Reported Outcome data will be summarized for the overall (unselected) population and within-stratum.
 
Pharmacokinetics:
 
Non-compartmental PK analysis will be performed for the PK population. The PK population will consist of patients in the first stage who have an evaluable PK profile, defined as a profile from which at least one of the PK parameters stated as endpoints can be estimated, and no protocol deviations that would affect the PK of antroquinonol. Descriptive statistics will be presented for all PK parameters. The PopPK methods will be used to estimate exposure metrics for patients with at least two plasma concentrations and sufficient and reliable dosing histories.
 
Tumor biomarkers:
 
The predictive value of tumor biomarkers will be assessed in appropriate subgroup analyses. Full details of this analysis will be provided in the Statistical Analysis Plan.
		
Date of the Protocol: 06 December 2017		

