9.2 Discussion of Study Design

9.2.1 Rationale for Single-Arm, Open-Label Phase II Study

This is a single-arm, open-label, Phase II study in KRAS-positive and KRAS-negative patients with stage IV (including pleural effusion) non-squamous NSCLC who have failed two lines of anti-cancer therapy. This is defined as patients with radiologically confirmed disease progression following greater than or equal to two, but less than or equal to four, prior lines of systemic anti-cancer therapy (see [Section 9.3.1](#) for a detailed description of the eligibility criteria). The rationale for this study is outlined in [Section 7.5](#) and described in more detail below.

The subject population of patients with stage IV (including pleural effusion) non-squamous NSCLC who have failed two lines of anti-cancer therapy was chosen for this study as there is a current unmet need to treat this population and results from the first-in-man Phase 1 study indicate that the tumor overall response at the end of treatment showed stable disease for all three patients (one patient in the 200 mg dose group and two patients in the 600 mg dose group) included in the per-protocol set (PPS). The PPS was defined in the Phase 1 study as all patients who completed at least three cycles of treatment with proper imaging assessment

(RECIST v.1.1). Furthermore, antroquinonol at 50, 100, 200, 300, 450, and 600 mg dose levels, given daily for 4 weeks, was generally safe and well tolerated, with no particular safety concerns or DLT being identified in the study.

Preclinical data (see [Section 7.3](#)) suggest that patients with KRAS mutation positive tumors may derive greater benefit from antroquinonol therapy. Hence, patients will be stratified according to KRAS mutation status.

An open-label design was selected as this was considered the most suitable design for evaluation of antroquinonol as a single agent in the patient population eligible for participation in this study.

A two-stage, single-arm design was chosen as this was considered most suitable for assessing the safety, tolerability, PK and efficacy of antroquinonol in patients who have previously failed two lines of anti-cancer therapy.

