14.3 Interim Analysis

An interim analysis for safety and efficacy will be performed when 20 patients overall and when 15 patients within each stratum are evaluable for the primary endpoint, PFS rate at 12 weeks. As described in [Section 14.1](#), if less than two patients are alive and progression-free within a stratum, then the accrual for that stratum will be discontinued. Otherwise, a maximum of 15 additional evaluable patients will be accrued to that stratum for a total of 30 evaluable patients. Furthermore, if less than three patients in the overall

(unselected) population are alive and progression-free in the first 20 evaluable patients, and the criterion for continuing the individual stratum are not met, then the accrual for all strata will be discontinued. Otherwise, a maximum of 40 additional evaluable patients will be entered (depending on whether any individual stratum is closed).

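### The overall 15-of-60 rule has no condition on stratum closure, so it can support further study in unselected patients after one KRAS stratum was closed for futility

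*Protocol*

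**What the plan says.** The synopsis (Statistical Methods) and Section 14.1 set two layers of rules.

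**Per stratum.** Each KRAS stratum starts with 15 evaluable patients. The condition for going on to 30 is: "If two or more patients are alive and progression-free at Week 12 within a stratum". Section 14.3 gives the converse: "if less than two patients are alive and progression-free within a stratum, then the accrual for that stratum will be discontinued". With 9 or more successes in 30, "then antroquinonol will be considered worthy of further study in that cohort".

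**Overall.** A separate rule addresses the overall (unselected) population. After a look at the first 20 evaluable patients, up to 40 more are entered, and the text notes that this number depends on whether a stratum has been closed. Then: "Fifteen or more patients alive and progression-free at Week 12 out of the maximum 60 evaluable patients would warrant further study".

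The null rate is 15% throughout. For the alternative, within each stratum "a PFS rate at 12 weeks of 40% and 35% overall (unselected) population will be of interest". Section 14.2.2.1 says that the primary analysis follows the procedure in 14.1, so this is the primary decision rule.

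No sentence ties the overall conclusion to both strata having stayed open. None says what becomes of the count of 15 when closure cuts the maximum from 60 to 45, or how an overall success is to be read beside a stratum that did not succeed.

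**The concern.** The primary objective (8.1) asks about unselected, KRAS-positive and KRAS-negative patients. Section 9.2.1 gives the reason for stratifying: the preclinical data "suggest that patients with KRAS mutation positive tumors may derive greater benefit from antroquinonol therapy". Unequal strata are therefore a possibility that the protocol itself raises, and early closure of one stratum is what the design provides for in that event.

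When a stratum closes at 15 patients and the other runs to 30, the pooled sample is two-thirds from the open stratum. A total of 15 can then come almost wholly from that stratum. As written, the plan would hold both that one half of the population was stopped for futility and that the population containing it warrants further study. At stake is whether the next trial enrols patients regardless of KRAS status.

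**Working it through.** **Inputs, all from the synopsis, 14.1 and 14.3.** Stratum: 15 patients, close if fewer than 2 successes, otherwise 30; success at 9 or more. Overall: at least 3 of the first 20, then 15 or more of 60. Null 15%; alternatives 40% (stratum) and 35% (overall). The unequal pairs of rates below are assumptions, because the protocol gives no separate expected rate for each stratum.

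**1. The plan's own figures.** Write b(n, x, p) for the binomial probability.
- Stratum: sum over x ≥ 2 of b(15, x, p) · P(Bin(15, p) ≥ 9 − x). This is 0.0276 at 15% and 0.9049 at 40%. Printed: 2.8% and 90.5%.
- Overall: sum over x ≥ 3 of b(20, x, p) · P(Bin(40, p) ≥ 15 − x). This is 0.0279 at 15% and 0.9558 at 35%. Printed: 2.8% and 95.6%.

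Each rule taken alone reproduces.

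**2. The two layers together.** Enumerate two independent strata, each stopped at 15 if it has 0 or 1 success and otherwise run to 30, and apply the total of 15. The 20-patient look is left out: its stop also requires that the stratum criterion is not met, and if both strata close the total is at most 2. The overall rule is met with probability 2.7% at 15%/15% and 94.6% at 35%/35%.

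**3. A result that shows the gap.** 1/15 (closed) + 14/30 = 15 of 45, so the count is reached. The open stratum supplies 30/45 = 67% of the sample instead of 30/60 = 50%.

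**4. How often.** Let q be the rate in the weaker stratum and T the total in the other stratum, at rate p, under its own two-stage rule. Then

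P(overall rule met and weaker stratum closed) = b(15, 0, q) · P(T ≥ 15) + b(15, 1, q) · P(T ≥ 14).

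- p = 40%: P(T ≥ 15) = 0.1754, P(T ≥ 14) = 0.2855.
 - q = 15%: 0.0874 × 0.1754 + 0.2312 × 0.2855 = 0.0153 + 0.0660 = 0.081.
 - q = 10%: 0.2059 × 0.1754 + 0.3432 × 0.2855 = 0.0361 + 0.0980 = 0.134.
- p = 50%: P(T ≥ 15) = 0.5722, P(T ≥ 14) = 0.7077.
 - q = 10%: 0.2059 × 0.5722 + 0.3432 × 0.7077 = 0.1178 + 0.2428 = 0.361.
- Both at 35%: 2 × (0.0016 × 0.0652 + 0.0126 × 0.1263) = 0.003.

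| True rates | Overall rule met | of which with a closed stratum | Met with both strata open |
|---|---|---|---|
| 15% / 15% | 2.7% | below 0.01 points | 2.7% |
| 35% / 35% | 94.6% | 0.3 points | 94.3% |
| 40% / 15% | 62.6% | 8.1 points | 54.5% |
| 40% / 10% | 44.6% | 13.4 points | 31.2% |
| 50% / 10% | 78.1% | 36.1 points | 42.1% |

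The last column is what remains if the overall conclusion requires both strata to have stayed open.

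**The case against.** **The overall and stratum questions are separate.** At 40% and 15% in equal strata the average rate is 27.5%, well above 15%, so meeting the overall rule is not a false positive about the average. This stands while both strata run to 30. It does not rescue the closed-stratum case, where the pooled sample is no longer half and half.

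**The wording may not reach a trial of 45.** The rule speaks of a maximum of 60, and one could argue that it does not apply after a closure. But the preceding sentence allows for a closed stratum, and no other threshold is given. If that reading is intended, the plan has no stated overall rule for a case it foresees, and it needs a sentence either way.

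**Error control is not harmed.** This is right. With a common 15% rate, 15 or more of 45 has probability 0.17%. A reader might infer that the printed 2.8% holds only when both strata are at 15%. The checks do not support that: for unequal strata averaging 15%, with closure applied, the rule is met in 2.3% (20%/10%), 1.5% (25%/5%) and 1.7% (30%/0%).

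**The trial is a Phase II screen with results reported by stratum.** A closed stratum would be visible to whoever plans the next study. That limits the consequence, but a pre-specified primary rule should not depend on later readers to set it aside.

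**Conclusion.** The gap is real and confined to decision logic. The printed significance levels and powers are correct. An overall success with a closed stratum is rare when the strata are alike (0.3% at 35%/35%) and not rare when they differ: 8.1%, 13.4% and 36.1% for the three assumed pairs. These sizes rest on the assumed unequal rates, independent strata of 15 then 30 patients, and the count of 15 still applying at 45.

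Two stronger readings are tempting and are not supported.
- A reader might treat a completed stratum observed below 15%, such as 4/30 beside 11/30, as one the plan had stopped. The sentence "Further testing will not be pursued if the PFS rate at 12 weeks is less than 15"% sets the null for the true rate. The operative stratum rules are fewer than 2/15 and at least 9/30, so 4/30 misses success but triggers no stop.
- A reader might infer that a drug active only in KRAS-positive tumours would usually be recommended for everyone. The overall rule is met in 62.6% at 40%/15%, but in 44.6% at 40%/10% and 28.2% at 40%/5%. The protocol says only that KRAS-positive patients may benefit more.

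**What to change.** In 14.1, 14.3 and the synopsis:

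1. State that 15 or more successes support further study in unselected patients only if both strata stayed open past Stage 1. If one was closed, the conclusion is limited to the open stratum under its own 9/30 rule.
2. State that when both strata complete but only one reaches 9/30, the overall result is a statement about the average rate and is reported together with both stratum conclusions. This is needed because item 1 does not remove disagreement. At 40%/15%, the overall rule is met with both strata open in 54.5%, and in 51.7 of those points the weaker stratum misses 9/30.

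A minimum observed rate in each completed stratum, such as 5/30, is not needed. It would be a new threshold without a basis in the plan.

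The cost is wording only, with no added patients. With closure applied, power at a uniform 35% goes from 94.6% to 94.3% (0.9461 − 0.0034 = 0.9427), and the false-positive rate at a uniform 15% stays at 2.7%.
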